4.1 Study Design

A feasibility prospective intervention trial (WP2) with qualitative assessment of participants' opinions of the acceptability of the intervention (WP3).

This protocol includes two work packages (WP2 & 3) which are part of a wider research programme focused on patellofemoral taping in OA. The wider programme comprises seven WPs which are summarised below. This protocol relates specifically to WP2 and WP3.

Prior to this protocol, WP1 was undertaken in January and February 2024. This involved 11 participants who were taken through the study concept, then shown the taping methods and planned training materials for the actual intervention study. This was a PPIE exercise to ensure the right questions were being asked, best methods used and that the planned study was meaningful. The findings from WP1 fully informed WP2 as described below.

WP2 is a feasibility open label trial of the taping intervention developed in WP1.

WP3 is a qualitative assessment of the acceptability of the taping intervention package (WP2) using semi-structured interviews and qualitative analysis.

WP1: Workshops: intervention development

WP2: Clinical trial: intervention delivery

WP3: Interviews: intervention acceptability

WP4: Generating impact: RCT

WP5: Dissemination

WP6: Follow on Clinical Trial

WP7: Project Management

4.2 Methods of Data Collection

Work Package 2 (WP2):

Once the eligible participants have been consented and recruited into the study, each participant will have an individualised taping technique determined by the immediate pain relief the tape provides (11). Taping will be demonstrated and applied to the participant. The length of tape will be calculated at 50% of the circumference of each subject's knee. We will provide two weeks' supply of pre-cut tape. Two strips of tape are applied across the front of the knee and patella dependent on each participant's preference and symptom change. Participants will then perform an activity that normally triggers their pain. They will decide if taping gives them immediate decrease in pain using a VAS pain score applied before and during the task with the tape. The tape technique with the best pain relief during the activity will be used for that subject for the taping intervention during the feasibility trial. Instructions in written, illustrative and video formats indicating the correct application of the patellar taping intervention have been developed by our PPIE group and two intervention development workshops (WP1). Participants will be asked to use the tape daily for 12 weeks. They will be advised on the amount of time daily they should wear the tape, what to do if the tape comes off and skin care. All subjects will receive advice, written information, and exercise instruction that aligns with best practice care for patients with knee OA and recommendations from NICE (18) and those available in the Osteoarthritis Guidebook

https://www.keele.ac.uk/media/keeleuniversity/ri/primarycare/pdfs/OA_Guidebook.pdf)

Participants will be assessed face-to-face at baseline and again face-to-face after 2 weeks and then by telephone or online (e.g. Zoom, Teams) at 6 and 12 weeks. At baseline and weeks 2, 6 and 12 subjects will complete the following assessments: Knee pain during a nominated aggravating activity (VAS_{NA} 0-10), the Knee Osteoarthritis & Injury Outcome Score for the patellofemoral joint (KOOS-PF) (20). Subjects will have a face-to-face assessment 2 weeks after treatment commences to check for correct application of the tape. At this 2 week visit a further 10 weeks of tape will be supplied. At each contact, participants will be asked about treatment adherence. They will be asked since the last timepoint (Baseline, or weeks 2, 6 or 12) approximately how many days per week and how many hours per day on average the tape was worn.

As there is no gold standard for measuring adherence to taping, we will estimate adherence by counting the number of unused strips of tape at the end of the trial and by asking how many days per week and how many hours per day on average the tape was worn. We will collect this information at the 2 weeks tape check and at the two telephone or online consultations at 6 and 12 weeks. Participants will be encouraged to adhere to the tape during the 6-week telephone call. Information on any adverse events will also be collected at each contact.

Work Package 3 (WP3):

Participants completing WP2 will all be given a PIS for WP3 and asked if they are interested in taking part in WP3. It will be explained that they may not be picked, depending on how many say yes as we will only require fifteen. Fifteen participants from the feasibility trial (WP2) will be invited to participate in one-to-one semi-structured interviews for WP3. Participants will be purposively recruited from those who consented to be contacted in WP2, to reflect a range of sex, age and ethnicity. It is anticipated that this sample size will be sufficient to generate rich data. However, recruitment will continue until data saturation has been achieved. Moreover, if data saturation is achieved before recruiting the fifteenth participant, recruitment will be stopped at that point. Purposive recruitment will allow us to include the voices of participants not commonly heard in this type of research, including those from underserved communities. As such, we are confident that purposively recruiting 15 participants is appropriate for this study. Semistructured interviews of approximately 60 minutes will be conducted to gain in-depth understanding of participants' experience of the intervention. Interviews will be informed by an interview guide developed from the findings of WP1, the research team including PPIE representative, underpinned by the Theoretical Framework of Acceptability (21) (see appendix 1). Participants will be interviewed by the research associate (RA) who is trained in undertaking qualitative interviews either in-person, online via Teams, or over the phone depending on the participants' preference. In-person interviews will take place in a private room at the [name], Manchester Metropolitan University. Two participants who will have taken part in the clinical trial will pilot the guide to ensure its appropriateness. Consent and demographic information will be collected at the start of the interview. Further discussion will be guided by each participant's response to the questions to allow exploration of unanticipated issues. Emerging findings from each interview will iteratively feed into subsequent interviews. Interviews will be digitally recorded, and interviews will be professionally transcribed.

Interviews will explore what went well and any barriers to adherence. This will help evaluate the performance of the participant treatment package. Currently, it is unclear how long taping can be used for effective treatment, so we will explore whether the number of hours of use is associated with a perceived reduction in knee pain and if there is a minimum threshold whereby a how long the tape must be used before any long-term pain reduction. Additionally, as there is no currently available evidence that tape is effective in the long-term specifically for PFJOA, we will explore participant views and willingness to be randomised in a future RCT.

Feasibility and adherence outcomes					
Measure	Stop	Edit	Go		
Number recruited	1 per month	2-3 per month	4 per month		
Percentage recruited (uptake)	< 25%	≥25% and < 75%	≥ 75%		
% of recruited participants with complete data	< 20%	≥20% and < 70%	≥ 70%		
% of recruited participants lost to follow-up at 12 weeks	> 20%	≤20% and ≥10%	< 10%		
% of recruited participants whose pain had clinically improved at 12 weeks	<20%	≥20 and <65%	≥65%		
% of recruited participants who would use the tape again	<20%	≤20 and ≥65%	≥65%		

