3.2 Outcome Measures

Primary outcome

 WP2: To assess recruitment to the study and retention: Participant uptake – number of participants recruited and number of participants who complete the study.

WP3: Report on participant experiences of taping and the trial process. Explore facilitators and barriers to adherence. Evaluate the performance of the participant treatment package.

Secondary outcomes (ii - vii)

- ii) To determine whether the tape can be applied by participants correctly at home: Clinical checks at 2 weeks recorded on the Clinical Report Form.
- iii) Adherence:
 - a. Number of returned or counted unused tapes
 - b. Number of days since the previous timepoint that participants report wearing the tape collected at weeks 2, 6 and 12.
 - c. Average number of hours the participants report wearing the tape daily since the previous timepoint at weeks 2, 6 and 12.
- (iv & v) To assess how to optimise adherence of taping over an extended period and to determine participants views about the acceptability of prolonged taping: Participants interviews in WP3.
- (vi) Effect of intervention: Reduction in pain

- (a) Knee pain measured by VAS_{NA} at baseline, 2, 6 & 12 weeks.
- (b) Knee pain and function measured by KOOS-PF at baseline, 2, 6 & 12 weeks.
- (vii) To determine a primary outcome for a large scale RCT and to inform sample size calculation: Analysis of quantitative data in vi a & b

4. Study Design and Methods of Data Collection

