4.6 Device in Use

The sports medical tape for this trial is widely used in UK clinical practice and is FDA approved and CE-marked. The tape is approved for use for the treatment of knee pain. It is budgeted for purchase within the study funding stream. Purchase orders will be raised by MFT, product will be shipped, once invoices are paid, to the Stopford Building/or Manchester CRF building and received by the Goods-In Department and delivered to the study team. Sufficient tape will be cut and distributed to the participants at the baseline and 2 weeks visits by the CI along with in person training plus the training materials submitted alongside this protocol. Any excess tape will be disposed of in general waste by the participants at home, information is in the PIS. The advice given will be that participants

should try and wear the tape for as long as is comfortable and taken off at night to be applied fresh the following day. There are no known complications with other treatments being used at the same time.

Manufacturer: We Tape

Brand: Rocktape UK: https://www.rocktape.co.uk

Distributer: c/o Fit Brands Ltd, [name]

This product is a class I medical device and is CE Marked. The CE mark is clearly visible on the outside of the packaging.

The product is made from 97% cotton and 3% nylon, it is hypoallergenic and it does not contain latex.

5. Study Sample and Recruitment

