5.2 Study Setting and Sample Identification

Participants will be identified by [name] and clinical team at the Manchester Local Care Organisation (MLCO) or by [name] in clinics at Salford Royal Hospital. Participants will be given a PIS to read and consider.

Those who are interested in taking part will be invited to attend a face-to-face baseline visit at the NIHR Manchester Clinical Research Facility. At the baseline visit potential participants will be asked to confirm that they have received and read this PIS. The researcher will further discuss the study with the potential participant and give an opportunity for them to ask questions.

If recruitment is not met by the above clinics an advert will be posted on the University of Manchester intranet and in the Manchester Evening News. This will invite potential participants to scan a QR code which leads them to some basic questions about their knee health and skin condition. If they are suitable, they will be given details to contact the research team.

The assessment and delivery of WP2 will take place in the NIHR Manchester Clinical Research facility. Participants will self-apply the taping intervention in their homes. The delivery of WP3 will take place in the Department of Health Professions at [name], Manchester Metropolitan University. Participants will be purposefully selected from those in the WP2 arm who have completed the 12 weeks programme by the CI and [name] from the Manchester Metropolitan University.

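### WP3 interviewees are sampled on demographics only, so nothing secures a range of tape use or pain response in interviews meant to explain adherence

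*Protocol*

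**What the plan says.** Section 4.2 (Work Package 3) sets the number: "Fifteen participants from the feasibility trial (WP2) will be invited to participate in one-to-one semi-structured interviews for WP3". It then sets the frame: interviewees are chosen purposively, from those who agreed in WP2 to be approached, "to reflect a range of sex, age and ethnicity". The only further aim given for the purposive approach is also about who people are, not how they used the tape: "Purposive recruitment will allow us to include the voices of participants not commonly heard in this type of research, including those from underserved communities".

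On stopping, the section says recruitment continues until saturation, and adds that "if data saturation is achieved before recruiting the fifteenth participant, recruitment will be stopped at that point". No condition is attached about which kinds of participant must have been interviewed by then.

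The task of the interviews is set in section 3.2, where WP3 stands under the primary outcome: "Explore facilitators and barriers to adherence". WP3 is also the named source for objectives iv (optimising adherence) and v (acceptability). Section 4.2 adds that the interviews will look at whether hours of use go with a perceived fall in knee pain, and whether there is a minimum amount of use.

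Days and hours of wear are collected at weeks 2, 6 and 12, and pain at baseline and the same weeks (section 4.2, Work Package 2). Section 5.2 places selection for interview after the 12-week programme.

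**The concern.** Purposive sampling should vary the characteristics that the research question turns on. Here these are how much the tape was worn and whether pain improved, and neither is in the frame. Fifteen people can be well spread on sex, age and ethnicity and still be mostly regular wearers whose pain improved.

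The saturation rule adds to this. In a group with similar experience, new themes may run out early, so interviewing could end before anyone who wore the tape little has been heard.

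At stake is the account of barriers and acceptability that WP3 passes to the design of the definitive trial. It could be thin where that trial most needs it. The question about hours of use and pain cannot be explored well without a spread on both.

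**Working it through.** The protocol gives no figure on this point, so there is none to reproduce. The calculation below illustrates how few low users the current frame could yield.

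**Inputs**
- WP2 sample 30 with 20% drop-out (section 5.3.1): 30 × 0.80 = 24 available.
- Interviews: 15 (section 4.2).
- Low users among the 24, *K*: not in the protocol. Assumed, with a range from 3 to 8.
- Selection unrelated to use, and all 24 willing: assumed.

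**Formula.** The number of low users heard, *X*, is hypergeometric: P(X = x) = C(n, x) × C(24 − n, K − x) / C(24, K), with n the number interviewed.

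**K = 4, n = 15.** C(24, 4) = 10,626.
- None: C(9, 4) = 126; 126 / 10,626 = 1.2%.
- Exactly 1: 15 × C(9, 3) = 15 × 84 = 1,260. At most 1: 1,386 / 10,626 = 13.0%.
- Exactly 2: C(15, 2) × C(9, 2) = 105 × 36 = 3,780. At most 2: 5,166 / 10,626 = 48.6%.

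**Range of K, n = 15** (expected number = K × 15/24)

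| Low users among 24 | Expected number heard | None | At most 1 | At most 2 |
|---|---|---|---|---|
| 3 | 1.9 | 4.2% | 30.8% | 77.5% |
| 4 | 2.5 | 1.2% | 13.0% | 48.6% |
| 5 | 3.1 | 0.3% | 4.7% | 25.5% |
| 6 | 3.8 | 0.1% | 1.5% | 11.3% |
| 8 | 5.0 | <0.1% | 0.1% | 1.3% |

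**Early saturation.** Suppose interviewing ends at 8 (assumed).
- K = 4: none in C(16, 4) / 10,626 = 1,820 / 10,626 = 17.1%. At most 1 in (1,820 + 8 × 560) / 10,626 = 6,300 / 10,626 = 59.3%.
- K = 6, with C(24, 6) = 134,596: none in 8,008 / 134,596 = 5.9%. At most 1 in (8,008 + 8 × 4,368) / 134,596 = 31.9%.

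**Unequal volunteering.** Suppose 30% of low users and 80% of the others volunteer (assumed).
- K = 6: 6 × 0.3 = 1.8 low users and 18 × 0.8 = 14.4 others. The share is 1.8 / 16.2 = 11.1%, or about 1.7 of 15 interviews, against 3.8 with equal volunteering.
- K = 8: 2.4 and 12.8. The share is 15.8%, or about 2.4 of 15, against 5.0.

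**Guaranteed number.** For every K up to 8, at least 16 other people are available to fill the 15 places, so the frame guarantees no low user at all.

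**The case against.** The case against is substantial. Fifteen of 24 is 62.5% of those available, so most low users would be interviewed by chance alone. With 4 low users, hearing at most 2 still means up to half of them were heard. The less favourable figures need low users to be rare, interviewing to stop at an assumed 8, or low users to volunteer less. If only 15 to 17 people agree, nearly all will be interviewed, and sampling variables can change little. The demographic frame is also a reasoned choice, given the stated aim of reaching underserved communities. Nor are the interviews the only source on barriers: section 6.1 collects reasons for unused tape at weeks 2, 6 and 12. All of this stands and limits the size of the point. None of it puts use or response into the frame.

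Two stronger readings are tempting but not supported.

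- *Selection bias by the CI.* Section 5.2 says "Participants will be purposefully selected from those in the WP2 arm who have completed the 12 weeks programme by the CI", and section 4.6 says "Sufficient tape will be cut and distributed to the participants at the baseline and 2 weeks visits by the CI". A reader might infer that interviewees will be chosen for good outcomes. But section 5.2 gives the selection jointly to a person from Manchester Metropolitan University, section 4.2 has a research associate do the interviews, and nothing suggests selection on outcome.
- *A skewed sample would be invisible in the report.* It need not be. Section 6.1 reports adherence for WP2 at each timepoint, and the interview guide in Appendix 1 asks how long the tape was worn, what hindered adherence, and whether the intervention did what it was meant to do.

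**Conclusion.** The point holds as a mismatch between the sampling frame and the question: WP3 must explain adherence and explore use against pain, but it is sampled and stopped without regard to either. Low users and non-improvers can be few; the text does not make that likely in every case.

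Under the assumptions of 24 available, 4 low users and 15 interviews drawn without regard to use, at most 1 is heard in 13% of samples and none in 1.2%. The risk is larger with early stopping or unequal volunteering. With 8 low users and all 15 interviews done it is negligible. The number of low users, the stop at 8 and the volunteering rates are all assumptions. The same arithmetic applies to non-improvers, whose number is also unknown.

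This is a worthwhile and cheap improvement, not an error that undermines WP3. It concerns sampling within the pool of completers; whether that pool should be wider is a separate question.

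**What to change.** In section 4.2 (Work Package 3):

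1. Add reported tape use (lower versus higher) and 12-week pain change (improved or not) as purposive sampling variables alongside sex, age and ethnicity. State what counts as lower use, since section 4.6 sets no target hours. Define improvement in the same way as for the pain criterion in the progression table.
2. Do not declare saturation until willing low users and non-improvers have been included where available. A fixed minimum per group is not needed: with few low users it could demand every one of them.
3. Report the tape use and pain change of interviewees next to those of all WP2 participants, so that readers can judge the spread.

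Both variables are already collected in WP2, so the change needs protocol wording and a short listing before selection. The cost is less freedom to fill demographic cells within 15 places, and possibly a few more interviews than an unconditional saturation stop would give. It cannot make low users volunteer, but step 3 would show if they did not.

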4.4 Schedule of Procedures

Work Package 2 (WP2):

Procedures	Visits				
Procedures	Baseline	Week 2*	Week 6*	Week 12*	
Informed consent	Х				
Demographics	х				
Intervention training	Х	x if required			
VAS / KOOS-PF	Х	х	Х	х	
Adverse Events		х	х	Х	
Observation of treatment		х			
Feedback on treatment		х	x	Х	
Telephone/online assessment			х	х	
WP3 Interview discussion				х	

^{*+/- 5} days

Work Package 3:

Procedures	
Flocedules	Single visit
Informed consent	x
Face to face, telephone or online interview	x

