5.3 Sampling

5.3.1 Size of Sample

This is a pragmatic sample size calculation for a feasibility study. A sample size of 30 is sufficient to allow estimation of feasibility parameters with 95% confidence intervals, including a drop out of 20% (19). A target of 50% for the primary outcome, participant uptake, can be estimated with 95% confidence intervals 36.8-63.2%.

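### The Edit band for willingness to use the tape again is an empty range, so results from 20% to just under 65% have no verdict; the source of the answer also needs stating

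*Protocol*

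**What the plan says.** Section 4.2 of the protocol closes with a table of six progression measures, each with Stop, Edit and Go limits. The last row reads "of recruited participants who would use the tape again <20% ≤20 and ≥65% ≥65" (percent): Stop below 20%, Edit at most 20% and at least 65%, Go at 65% or more. The row above it, on clinically improved pain at 12 weeks, has the same Stop and Go limits and gives Edit as at least 20% and below 65%.

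The denominator of the last row is explicit: "of recruited participants who would use the tape again". Section 5.3.1 sets the number: "A sample size of 30 is sufficient to allow estimation of feasibility parameters with 95% confidence intervals, including a drop out of 20" percent.

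On where the answer comes from:

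- Section 3.2 lists no outcome on using the tape again. It covers acceptability by a different route: "to determine participants views about the acceptability of prolonged taping: Participants interviews in WP3".
- Section 4.2 says of those interviews: "Fifteen participants from the feasibility trial (WP2) will be invited to participate in one-to-one semi-structured interviews for WP3". Section 5.2 adds that they are chosen from people who have completed the 12 weeks.
- The WP2 schedule in section 4.4 has a row "Feedback on treatment" at weeks 2, 6 and 12, without saying what is asked.
- The Appendix 1 interview guide has no item on using the tape again. Its one willingness item concerns allocation in a future RCT.

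**The concern.** A progression table is useful because it fixes the verdict before the data are seen. Here the middle verdict cannot be reached by any result, and the middle is where a moderate response would fall. The team would then have to choose a label after seeing the figure, which is what the table is meant to prevent.

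The secondary concern is the match between numerator and denominator. The row is a share of everyone recruited, but the text shown does not say when the question is put or to whom. The percentage means one thing if all WP2 participants are asked and another if only a selected subset of completers is asked. The row is not the primary outcome, but of the six it comes closest to measuring whether participants accept the treatment, and the stated aim concerns acceptability as well as feasibility.

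**Working it through.** **Inputs.** Limits of 20% and 65% (table in section 4.2); 30 recruited (section 5.3.1); 15 interviews (section 4.2, WP3); dropout allowance of 20% (section 5.3.1), so 30 × 0.80 = 24 completers.

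**The plan's own figure.** Section 5.3.1 says that 50% uptake "can be estimated with 95% confidence intervals 36.8-63.2" percent. An exact (Clopper-Pearson) interval for 30 of 60 gives 36.8% to 63.2%, so the figure can be reproduced. The 60 approached is my inference and is not stated. With 30 as the denominator the exact interval would be 31.3% to 68.7%. This figure concerns uptake, and nothing below depends on it.

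**Step 1: grade every count as printed.** Let k be the number of 30 who say yes.

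| Band | Condition | Counts |
|---|---|---|
| Stop | k/30 < 0.20, so k < 6 | 0 to 5 |
| Edit | k/30 ≤ 0.20 and k/30 ≥ 0.65, so k ≤ 6 and k ≥ 19.5 | none |
| Go | k/30 ≥ 0.65, so k ≥ 19.5 | 20 to 30 |
| No verdict | remainder | 6 to 19 |

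The uncovered counts run from 6/30 = 20.0% to 19/30 = 63.3%. They are 19 − 6 + 1 = 14 of 31 possible results. Exactly 20% is among them, because Stop is strictly below 20%.

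**Step 2: try reading 'and' as 'or'.** Edit would then cover 0 to 6 and 20 to 30. It would overlap all of Stop and all of Go, and still leave 7 to 19 uncovered. This reading does not rescue the cell.

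**Step 3: how often the gap would matter.** Take 30 independent answers with true rate p. The chance of no verdict is the sum over k = 6 to 19 of C(30,k) p^k (1−p)^(30−k).

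| True rate p | Chance of no verdict |
|---|---|
| 20% | 0.57 |
| 40% | 0.99 |
| 50% | 0.95 |
| 60% | 0.71 |
| 65% | 0.49 |
| 70% | 0.27 |

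The protocol gives no expected rate, so p is shown over a range.

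**Step 4: apply the band from the row above.** With Edit at 20% or more and below 65%, 30 recruited give Stop 0 to 5, Edit 6 to 19 and Go 20 to 30, so each count is graded exactly once. With 24 as the denominator the bands are Stop 0 to 4, Edit 5 to 15 and Go 16 to 24, again complete. Merely swapping the two signs (at least 20 and at most 65) would make Edit and Go overlap at exactly 65%. That value cannot occur with 30 recruited (0.65 × 30 = 19.5) but can with other totals, for example 13 of 20. The upper limit therefore needs to be strict.

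**Step 5: what the source of the answer could change.** If only 15 interviewees were asked and all said yes, the share of 30 recruited would be 15/30 = 50%, short of 65%. The same answers would be 15/24 = 62.5% of completers and 15/15 = 100% of interviewees. This step assumes collection in WP3 only, which the protocol does not state.

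**The case against.** The strongest reply is that this is a slip of the signs and that nobody would be misled. With Stop and Go fixed at 20% and 65%, Edit can only be what lies between, and the row above prints exactly that. This stands as to intent and makes the correction easy. It does not make the printed rule valid. Damage in converting the table from PDF is also unlikely, since the neighbouring rows are intact. The loss-to-follow-up row uses the 'at most … and at least' form correctly, because there low values are favourable.

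Four stronger readings are tempting, and the documents do not support them:

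- **That the row cannot be graded at all.** Stop and Go are clear and mutually exclusive. Only the middle lacks a verdict.
- **That nothing in the trial collects the answer.** The schedule entry "Feedback on treatment" applies to WP2 participants at three contacts and could carry the question. Case report forms and questionnaires are not reproduced in full, and a protocol need not print every item. What stands is that no outcome or interview item names the question and that the content of this procedure is undefined in the text shown.
- **That Go is out of reach because only 15 people answer.** Nothing says the question is confined to the interviews, and the wording of the row points to all WP2 participants. Nor is 15 a firm maximum: the study summary gives it as approximate, and section 4.2 lets interviewing continue, or stop sooner, according to saturation.
- **That the acceptability half of the research question fails.** The protocol does not label this row as acceptability, and the WP3 thematic analysis addresses acceptability whatever this cell says.

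It is also fair to say that the treatment of non-response may be left to a statistical analysis plan, and that counting silence as a 'no' would have to be squared with section 6.1, which rules out imputation.

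**Conclusion.** The Edit cell is wrong as written. For 30 recruited, 14 of 31 possible counts (6 to 19, or 20.0% to 63.3%) receive no verdict. The chance of landing there is about one half or more for each true rate examined from 20% to 65%, assuming independent answers and an answer from all 30. Results below 20% or at 65% and above are unaffected. The intended band is almost certainly at least 20% and below 65%, inferred from the row above.

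The second part is smaller and mostly a matter of missing detail: the row has a stated denominator but no stated question, timing or respondents. A reader might infer a ceiling of about 50%. That holds only if collection were limited to about 15 interviews out of 30 recruited, which the protocol does not say, so it is a reason to specify the source and not evidence that the criterion fails.

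No sample size, safety rule or estimate is affected, and the percentage can be reported whatever the cell says. What is affected is the pre-set decision attached to it.

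**What to change.** 1. In the section 4.2 table, change the Edit cell of the last row to at least 20% and below 65%, with the upper limit strict, as in the row above.
2. State that every WP2 participant is asked one fixed yes/no question on whether they would use the tape again, at the existing week-12 contact or at the last contact for anyone who leaves earlier. Name it in section 3.2, and in section 4.4 under the existing feedback entry or as its own line.
3. Keep all recruited participants as the denominator, as the row says, and report the number without an answer beside the percentage. If non-answers are to count as anything other than missing, say so and reconcile it with the no-imputation statement in section 6.1.

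The cost is one corrected cell and at most one short question at contacts that already take place, with no change to sample size or visits. Both changes should be made before results on this item are seen.
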